2.8 Safety analyses

Safety assessments will be based mainly on the frequency of adverse events. Adverse events will be coded by primary system organ class and preferred term according to the Medical Dictionary for Regulatory Activities (MedDRA). An adverse event related to study drug is defined as one considered by the investigator to have a suspected relationship with the study drug. The adverse events will be summarized by the number and percentage of patients in each primary system organ class and preferred term. For summaries by severity of event, the most severe occurrence for a particular preferred term will be used for a given patient. Summary tables of adverse events by treatment and severity will be provided.

Multiple occurrences of the same AE or SAE in the same patient will be counted only once, using the worst severity and drug relationship.

In the data listings of adverse events, the severity of an AE, whether or not an AE is study drug related, and whether or not it is a serious AE, will be indicated.

Abnormal laboratory values or test results constitute adverse events only if they induce clinical signs or symptoms or require therapy.

Laboratory data will be summarized by presenting summary statistics of raw data and change from baseline values (means, medians, standard deviations, ranges) and by presenting number and percentage of patients with notable laboratory abnormalities according to Appendix 1.

Data from other tests (vital signs) will be listed, notable values will be flagged, and any other information collected will be listed as appropriate.

All safety analysis will be based on SAF.

2.8.1 Adverse events (AEs)

Any AE occurred during the study period will be included in AE summary tables, i.e. AEs occurred in screening phase and double blind period and SAE up to 30 days after the study completion.

The MedDRA version used for reporting the study will be described in a footnote.

Within each reporting phase, the following rules are applicable. If a subject reported more than one adverse event with the same preferred term, the adverse event with the greatest severity will be presented. If a subject reported more than one adverse event within the same primary system organ class, the subject will be counted only once with the greatest severity at the system organ class level, where applicable. Statistical analyses, which will only be performed for the double blind or later phase, will include all post-baseline AEs up to and including the analysis cut-off (AEs up to the final visit and SAEs up to 30 days after the final visit for each patient) irrespective of how long after the last day of study treatment they occurred.

The number and percentage of subjects reporting any adverse event during reporting will be summarized by primary system organ class, preferred term and treatment. The most common adverse events reported ($\geq 1\%$ in any group for each preferred term in the SOC-PT table) will be presented in descending frequency according to its incidence in the LCZ696 group starting from the most common event.

Separate summaries will be provided for study medication related adverse events, death, serious adverse events, other significant adverse events leading to study discontinuation and adverse events leading to dose adjustment.

The following summaries will be generated for AEs during the double blind period:

- All adverse events
- Serious adverse events
- Adverse event by severity grade
- Adverse events causing study drug discontinuation
- Adverse events requiring dose adjustment or study-drug interruption
- Investigator reported causes of deaths by primary system organ class and preferred Term

The above information also be listed. Analysis will be based on SAF.

2.8.1.1 Adverse events of special interest / grouping of AEs

AEs of special interest will be summarized separately in addition to the above analysis. The following are the AEs of special interest: angioedema events and angioedema-like events, dementia-related events, hepatotoxicity (drug related hepatic disorders) and statin-related events (only rhabdomyolysis, acute pancreatitis, myalgia and muscle spasm). The information will also be listed. Analysis will be based on SAF.

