Exclusion criteria	
 ▪ History of hypersensitivity or allergy to any of the study drugs, drugs of similar chemical classes, ACEIs, ARBs, or NEP inhibitors as well as known or suspected contraindications to the study drugs ▪ Previous history of intolerance to recommended target doses of ACEIs or ARBs ▪ Known history of angioedema ▪ Requirement of treatment with both ACEIs and ARBs ▪ Current acute decompensated HF (exacerbation of chronic HF manifested by signs and symptoms that may require intravenous therapy) ▪ Symptomatic hypotension and/or a SBP < 100 mmHg at Visit 1 (screening) or at Visit 3 (randomization) ▪ Estimated GFR < 30 mL/min/1.73m² as measured by the simplified MDRD formula at Visit 1 (screening), or Visit 3 (randomization) ▪ Serum potassium > 5.2 mmol/L at Visit 1 (screening) or at Visit 3 (randomization) ▪ Acute coronary syndrome, stroke, transient ischemic attack, cardiac, carotid or other major CV surgery, percutaneous coronary intervention (PCI) or carotid angioplasty within the 3 months prior to Visit 1 ▪ Coronary or carotid artery disease likely to require surgical or percutaneous intervention within the 6 months after Visit 1 ▪ Patients with severe obesity (Adipositas permagna – BMI ≥ 40) ▪ Pregnant or nursing (lactating) women
Investigational and reference therapy	
 • LCZ696 200 mg bid • Enalapril 10 mg bid
Efficacy assessments	
Primary assessment:
 
 • change of VO_{2peak} compared to baseline measurements (adjusted to body weight) after 3 months 
Secondary assessments:
 
 • change of VO_{2peak} compared to baseline measurements (adjusted to body weight) after 6 weeks of treatment

	
 • Change of VE/VCO₂ slope after 6 weeks and 3 months of treatment • Change in exercise capacity (Watt) at ventilatory anaerobic threshold (VAT) after 6 weeks and 3 months of treatment • Change in rate of perceived exertion during exercise (Borg Scale) after 3 months of treatment
Safety assessments	
 • AEs and SAEs • Sitting systolic (SBP) and sitting diastolic BP (DBP) • Symptomatic hypotension • Angioedema • Laboratory values • Hyperkalemia • Renal dysfunction
Other assessments	

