3.2 Rationale of study design

There is a general agreement that apart from reducing the major fatal and non-fatal consequences of HF with a reduced LVEF, i.e., CV death and hospitalization for worsening HF, improving exercise capacity, daily physical activity and quality of life is crucial in patients with CHF. Thus, measurement of VO_{2peak} (adjusted to body weight) as assessed by cardiopulmonary exercise testing (CPET) in patients with chronic heart failure will be the primary endpoint of this study. This endpoint is established for assessing activity levels of patients. Moreover, the study design is reasonable and adapted from recent studies in treatment of patients with CHF in terms of investigational treatment, duration of assessment period and the comparator is established as standard of care in those patients. The study design is also in line with all required safety assessments and follow-ups for patients with CHF and for the treatment with LCZ696 and in compliance with the effective risk management plan for the product. Thus, events of angioedema, liver events, statin related events, and events of cognitive impairment are followed up by targeted questionnaires. Pregnancies during the study are also followed to capture outcome. Please refer to [Section 6.5](#) (safety assessments) for further details. Known risks of hypotension, renal impairment, and hyperkalemia are closely monitored to prevent severe events and are subject to separate guidance should such events occur. Please refer to [Sections 6.5.2](#) and [6.5.4](#) for assessments of blood pressure and laboratory assessments, respectively; and to [Sections 14](#), [15](#), and [16](#) for guidance to manage these risks.

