6.5.7 Angioedema

Angioedema is a type of abrupt swelling that occurs under the skin and/or mucous membranes and is often localized to the head, neck, throat, and/or tongue, but may occur elsewhere, including the genitalia and intestines. Severe cases may be associated with airway compromise. Although, the mechanism is not fully understood, bradykinin has been implicated as the putative mediator. Therefore, medications that raise the levels of endogenous bradykinin by inhibiting the enzymes responsible for its breakdown, such as ACE, aminopeptidase P, and NEP, may result in this potentially dangerous side effect.

It is important that the investigator pays special attention to any swelling or edema that may resemble angioedema or angioedema-like events that may be reported by patients. If such an event occurs, the investigator will complete an Adjudication Questionnaire for an Angioedema-like Event form (provided by Novartis) to summarize the event, its treatment, and its ultimate outcome. This report along with the requisite medical documentation must be submitted to Novartis as soon as possible. Follow-up reports must be communicated to Novartis as soon as new information regarding the event becomes available. All hospital records related to the event must be communicated to Novartis.

The investigator may be also be contacted by Novartis regarding AEs that may resemble an angioedema-like event. A list of terms that are considered “angioedema-like” (e.g., periorbital swelling) will be provided to sites in a manual. The investigator or his/her delegated staff must

complete the required forms and provide the required medical records for all such events, regardless of whether the investigator views the event in question as angioedema or not.

All angioedema reports will be forwarded to an Angioedema Adjudication Committee by Novartis for assessment. Information regarding this committee is outlined in [Section 8.5](#). Details on the procedures for reporting angioedema events will be provided to investigators in a manual.

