6.5.9 Statin-related Events

[figure not shown]
Statin-related events are subject to additional safety assessments and thus are followed with a standardized questionnaire. A list of terms that are considered “statin-related” (e.g., rhabdomyolysis, acute pancreatitis, myalgia and muscle spasm) will be provided to sites in a manual.

If such an event occurs that meets criteria for serious adverse event, the investigator will complete a separate questionnaire for a Hepatotoxicity and Statin-related Event form (provided by Novartis) to summarize the event, its further diagnostic tests performed, and its related information.

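### SAP 2.8.1.1 closes the statin-related group at four terms that the protocol gives only as examples, and does not separate committee-confirmed from reported angioedema

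*SAP*

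**What the plan says.** **Categories.** Protocol 3.2 states that "events of angioedema, liver events, statin related events, and events of cognitive impairment are followed up by targeted questionnaires". SAP 2.8.1.1 takes up the same four: "The following are the AEs of special interest: angioedema events and angioedema-like events, dementia-related events, hepatotoxicity (drug related hepatic disorders", followed by the statin-related group.

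**Statin-related events.** The SAP defines the group as "statin-related events (only rhabdomyolysis, acute pancreatitis, myalgia and muscle spasm". Protocol 6.5.9 names the same four terms differently: they illustrate a list, "e.g., rhabdomyolysis, acute pancreatitis, myalgia and muscle spasm) will be provided to sites in a manual".

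**Angioedema.** Under protocol 6.5.7, sites complete the forms for every angioedema-like event, even one that the investigator does not regard as angioedema. It adds: "All angioedema reports will be forwarded to an Angioedema Adjudication Committee by Novartis for assessment". Protocol 8.5 leaves the committee's responsibilities to a separate document. SAP 2.8.1.1 names angioedema and angioedema-like events and says they will be summarized. The readable SAP text does not mention the committee or its outcome.

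**Hypotension.** The protocol synopsis lists "Symptomatic hypotension" among the safety assessments, and protocol 3.2 says: "Known risks of hypotension, renal impairment, and hyperkalemia are closely monitored to prevent severe events". SAP 2.8.3.4 gives renal dysfunction and hyperkalemia their own laboratory analyses. SAP 2.8.4.2 summarizes sitting blood pressure by visit. The readable text defines no hypotension event or term group.

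**The concern.** The special-interest tables are where a reader will look for the event groups that the sponsor singled out for follow-up, and safety and tolerability is a stated secondary objective (SAP 1.2.2).

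For statins, examples have become the whole definition. A programmer who follows the SAP exactly will leave out any coded event that is on the manual's list but is not one of the four terms. The protocol has a reason to watch this group: section 5.5.8 reports that co-administration raised the peak concentration of atorvastatin and its metabolites by 68% to 108%, although total exposure was not significantly changed (less than 34%).

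For angioedema, broad capture followed by expert assessment is useful only if both layers can be seen. If the tables show only what was reported, unspecific swelling in heart-failure patients cannot be told apart from confirmed angioedema.

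If either definition is settled after unblinding, the choice is open to challenge.

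**Working it through.** The plan gives no figure on this point to reproduce. The check is a comparison of texts, with simple arithmetic for size.

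**Step 1: the texts side by side.**

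| Topic | Protocol | SAP | Result |
|---|---|---|---|
| Categories | Four questionnaire topics (3.2) | The same four (2.8.1.1) | Agree |
| Statin-related terms | Four examples of a manual list (6.5.9) | The same four, as a closed list (2.8.1.1) | Differ |
| Angioedema | Broad reporting, then committee (6.5.7, 8.5) | Both event types named, no confirmed/reported split (2.8.1.1) | SAP silent |
| Hypotension | Named safety assessment and known risk (synopsis, 3.2) | Visit summaries of blood pressure (2.8.4.2) and general AE tables (2.8.1) | No event group |
| Analysis of these groups | None specified (9.5.2) | 2.8.1.1 | SAP adds to the protocol |

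**Step 2: what the statin restriction loses.** The protocol's *e.g.* implies that the manual holds more than four terms, but the manual is not available, so the number omitted cannot be computed. Let *k* be the patients in an arm whose only statin-related event is coded to a manual term outside the four. The grouped row is then short by 100 × *k*/*n* percentage points. With the planned *n* = 100 per arm (protocol 9.7) and *k* assumed:

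- *k* = 0: 100 × 0/100 = 0 points
- *k* = 1: 100 × 1/100 = 1 point
- *k* = 2: 100 × 2/100 = 2 points

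**Step 3: what remains elsewhere.** SAP 2.8.1 tabulates all adverse events by system organ class and preferred term. The table of most common events uses a threshold of 1% in any group, which is one patient at 100 per arm (1/100 = 1%). Creatine kinase is among the laboratory tests analysed (SAP 2.8.3.2). A rise of more than 300% is a notable value (SAP Appendix 1), counted by patient (SAP 2.8.3). The loss is therefore in the grouped patient count, not in the individual events. That count cannot be rebuilt by adding preferred-term rows, because one patient may appear in several.

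**Step 4: angioedema.** Take one reported angioedema-like event in an arm of 100 (assumed). The reported row is 1/100 = 1%. The confirmed row is 0% if the committee rejects the event and 1% if it accepts it. Without a split, the reader cannot tell which.

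**Step 5: hypotension.** Assume 10 patients in an arm of 100 with symptomatic hypotension. If all are coded to one preferred term, that row shows 10%. If they are spread evenly over four terms, 10/4 = 2.5 patients per term, so the rows show 2% or 3%. The true spread is unknown.

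**The case against.** The strongest reply is that the SAP contradicts nothing. Its four categories are those of protocol 3.2. Protocol 9.5.2 specifies no special-interest table, no hypotension group and no analytic use of adjudication, so the SAP goes beyond the protocol. For that reason, the absence of an entry in SAP section 4 is not in itself a breach. This stands. A reader might infer that the SAP's special-interest categories do not match the protocol, but the texts do not support that.

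On statins, the manual's list serves to trigger a questionnaire when an event is serious (protocol 6.5.9). It is not stated to be an analysis set. A reader might also infer that terms such as myopathy or raised creatine kinase are dropped. No document shows that either is on the list, and creatine kinase is analysed as a laboratory value. Both replies stand. What survives is that the SAP uses the same group name and turns examples into a closed definition without giving a reason.

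On angioedema, the SAP names two event types and does not say that they share one row. Protocol 6.5.7 says only that reports go to the committee for assessment, and nothing shows that its outcome is held in the study database. It would go too far to say that the SAP pools the events or rejects the committee's finding. The fair statement is that it is silent on a confirmed/reported split.

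On hypotension, the protocol never labels it an event of special interest. SAP 2.8 says that notable vital signs will be flagged, and SAP 2.8.1 tabulates events that led to dose adjustment, interruption or discontinuation. However, the SAP's notable-value appendix covers laboratory tests only, and tables by preferred term do not give one count of patients with hypotension. This is an omission rather than a contradiction.

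**Conclusion.** The point holds in a limited form. The firmest part is the statin-related definition: a stated SAP rule, followed exactly, can undercount the group that the protocol describes. The size is 1 percentage point per affected patient at 100 per arm. The number of patients and terms affected is unknown, because the manual cannot be seen, and it could be zero. It would be wrong to state that an undercount will occur.

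The angioedema part also stands, as an inexpensive improvement: the protocol sets up adjudication, and the readable SAP gives the outcome no place in the tables. This rests on the readable text. Some later SAP sections are blacked out, but 2.8.1.1, which defines the groupings, can be read in full.

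Hypotension is a lesser suggestion. Of the three known risks that protocol 3.2 names together, it is the only one without a dedicated SAP analysis.

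All these tables are descriptive. No test changes, and the primary inference is unaffected.

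**What to change.** In SAP 2.8.1.1, before unblinding:

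1. Define the statin-related group by the manual's full term list, and attach or cite the list version. If the restriction to four terms is intended, record it with its reason in SAP section 4.
2. Show angioedema in two rows by arm: events confirmed by the Adjudication Committee, and events as reported. This depends on the committee's outcome being transferred to the study data. If it will not be, say so and label the row as reported events.
3. As an optional addition, pre-specify a preferred-term group for hypotension, counted by patient and arm.

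The cost is SAP wording, up to two term lists (statin-related and hypotension), a little extra programming and possibly one data transfer for the committee's outcome. Items 1 and 3 use adverse events that are already being collected and coded.

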2.8.2 Deaths

Death will be summarized by number and percentage of patients in each primary system organ class and preferred term based on SAF.

2.8.3 Laboratory data

Laboratory data will be summarized for double blind period based on the SAF and also be listed.

Laboratory data for hematology (including hemoglobin, hematocrit, red blood cell count(RBC), white blood cell count with differential (WBC), and platelet count), and blood chemistry (including Blood urea nitrogen (BUN), glucose, creatinine, total bilirubin, AST (SGOT), ALT

(SGPT), alkaline phosphatase, sodium, potassium, chloride, calcium, HbA_{1c}, total protein, albumin, uric acid, and lipid profile, estimated glomerular filtration rate (eGFR)) will be summarized by treatment.

The eGFR is calculated according to the formula:

$$\text{eGFR (mL/min/1.73 m}^2\text{)} = 175 \times (\text{Serum creatinine}/88.4)^{-1.154} \times (\text{Age})^{-0.203} \\ \times (0.742 \text{ if female}) \times (1.212 \text{ if black}),$$

where serum creatinine is in $\mu\text{mol/L}$ (SI unit) and age is non-rounded at the time of the laboratory sample in years.

Descriptive summary statistics (mean, median, standard deviation, min and max) for the change from baseline to each study visit will be presented. These descriptive summaries will be presented by laboratory test and treatment group. Change from baseline will only be summarized for subjects with both baseline and post-baseline values and will be calculated as defined in section 2.1.1.

The number and percentage of subjects with clinically notable laboratory results after baseline will be presented. Clinically notable laboratory results, for those parameters where ranges are available, are given in [appendix 1](#) below. For the calculation the denominator are based on the evaluable post-baseline subjects who did not have the notable abnormality at baseline from the central laboratory.

2.8.3.1 Hematology

Hematology tests performed may include the following:

- Hemoglobin
- Hematocrit
- RBC
- WBC count with differential
- Platelet

The above tests will be analysed at visit 1 and 7.

2.8.3.2 Clinical chemistry

Blood Chemistry tests performed may include the following:

- Blood urea nitrogen (BUN)
- Creatine kinase (CK)
- Glucose
- Creatinine
- Total bilirubin (TBL)
- AST (SGOT)
- ALT (SGPT)

- Alkaline phosphatase (ALP)
- Sodium
- Potassium
- Potassium
- Calcium
- Hemoglobin A1C
- Total protein
- Albumin
- Uric acid
- Lipid profile

The above tests will be analysed at visit 1 and 7.

- Thyroid-stimulating hormone (TSH) will be assessed at Visit 1 only.

BUN, serum potassium, and serum creatinine value for eGFR calculation will be obtained from patients at every visit when a complete laboratory test is not done (i.e., Visits 3-5).

